6.3. Early Termination Visit and Follow-up Visit

All patients withdrawing from the study prior to Week 52 will complete an Early Termination visit. The Early Termination visit procedures are identical to those of Week 52; however, for patients whose last dose of study drug is during Week 32 or earlier, the following procedures do not need to be performed: transvaginal ultrasound (with or without a transabdominal ultrasound), bone densitometry, and endometrial biopsy. These procedures may be performed at the investigator's discretion if they aid in follow-up of ongoing adverse events.

Patients (including those who complete the Week 52 visit and those who withdraw early from this study) will have a Follow-up visit approximately 30 days after the last dose of study drug, or prior to the date of initiation of another investigational agent or hormonal therapy affecting the hypothalamic-pituitary-gonadal axis or surgical intervention or other invasive procedure for uterine fibroids, whichever occurs first. However, for patients who enroll directly into another relugolix clinical study upon completion of the Week 52 visit, then the Follow-up visit may be waived.

The Follow-up visit will be used to assess safety after discontinuation of study treatment including adverse events, clinical safety laboratories, and return of menstruation. Refer to the Schedule of Activities (see Section 1.1) for individual study visit procedures during the Follow-up visit.

At an Early Termination visit occurring on or after Week 36, patients with a bone mineral density loss of > 3 relative to the parent study Baseline measurement will undergo a follow-up bone densitometry scan at 6 (± 1) months and will be contacted to question them about medications and conditions (eg, pregnancy) that might affect bone mineral density through the time of follow-up bone densitometry. If Early Termination occurs prior to Week 36, follow-up bone densitometry will be performed according to the requirements of the parent study. The follow-up bone densitometry will be submitted for central reading.

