4.3.8. Visit Windows

Visit windows, which will be used to associate assessments with a scheduled visit, will be used only for summarizing data by visit. The windows for scheduled assessments are shown in [Table 2](#), [Table 3](#) (BMD), [Table 4](#) (electrocardiogram [ECG]), [Table 6](#) (UFS-QoL), and [Table 6](#) (transvaginal ultrasound and EQ-5D-5L) respectively. For safety assessments, the study day will be used to determine the associated visit window. There will be no separation of data from the parent and extension study. For example, if an assessment in the extension study falls in the Week 24 visit window, it will be summarized as Week 24.

If the results from more than one assessment are within a given visit window, the non-missing result from the assessment closest to the target date will be used. If two assessments are equally close to the target day, the earlier assessment will be used. For summaries of shift from Baseline in safety parameters, all values will be considered for these analyses.

Table 2: Visit Windows for Monthly Assessments

Visit	Start Day	Target Day	End Day
Week 4 ^a	1	29	43
Week 8	44	57	71
Week 12	72	85	99
Week 16	100	113	127
Week 20	128	141	155
Week 24	156	169	183
Week 28	184	197	211
Week 32	212	225	239
Week 36	240	253	267
Week 40	268	281	295
Week 44	296	309	323
Week 48	324	337	351
Week 52	352	365	Date of last dose + 6 ^b
Safety Follow-Up ^c	Date of last dose + 7 days	Date of last dose + 30 days	Date of last dose + 60 days

^a Start day of Week 4 for study day 1 includes only post-Baseline assessments that occurred after the first dose.

^b End day of Week 52 is date of last dose + 1 for patients entering the MVT-601-035 study.

^c The safety follow-up visit window will be restricted to assessments prior to the date of initiation of another investigational agent or hormonal therapy affecting the hypothalamic-pituitary-gonadal axis or surgical intervention for uterine fibroids.

Table 3: Visit Windows for Bone Mineral Density Assessments

Visit	Start Day	Target Day	End Day
Week 12	64	85	106
Week 24	148	169	196
Week 36	197	253	308
Week 52	309	365	421

Assessments will be excluded from analysis if they occur on or after the date of initiation of another investigational agent or hormonal therapy affecting the hypothalamic-pituitary-gonadal axis or surgical intervention for uterine fibroids. Assessments after date of last dose of extension study drug + 30 days will also be excluded from analysis.

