Table 4: Visit Windows for Week 12, 24, and 52 Assessments (ECG)

Visit	Start Day	Target Day	End Day
Week 12	64	85	106
Week 24	148	169	196
Week 52	309	365	421

Table 5: Visit Windows for Week 12, 24, 36, and 52 Assessments (UFS-QoL)

Visit	Start Day	Target Day	End Day
Week 12	64	85	106
Week 24	148	169	196
Week 36	197	253	308
Week 52	309	365	421
Safety Follow-up ^a	Date of last dose + 7 days	Date of last dose + 30 days	Date of last dose + 60 days

^a The safety follow-up visit window will be restricted to assessments prior to the date of initiation of another investigational agent or hormonal therapy affecting the hypothalamic-pituitary-gonadal axis or surgical intervention for uterine fibroids.

Table 6: Visit Windows for Week 24 and 52 Assessments (Transvaginal Ultrasound, EQ-5D-5L, Endometrial Biopsies)

Visit	Start Day	Target Day	End Day
Week 24	128	169	196
Week 52	309	365	421
Safety Follow-up ^a	Date of last dose + 7 days	Date of last dose + 30 days	Date of last dose + 60 days

^a The safety follow-up visit window will be restricted to assessments prior to the date of initiation of another investigational agent or hormonal therapy affecting the hypothalamic-pituitary-gonadal axis or surgical intervention for uterine fibroids.

Table 7: Time Window for Feminine Product Collection

Visit	Feminine Product Collection Visit Date ^{a,b}	Time Window ^a
Week 28	X_1	(Date of Extension Study Day 1) - < X_1
Week 32	X_2	$(X_1 + 1) - \leq X_2$
Week 36	X_3	$(X_2 + 1) - \leq X_3$
Week 40	X_4	$(X_3 + 1) - \leq X_4$
Week 44	X_5	$(X_4 + 1) - \leq X_5$
Week 48	X_6	$(X_5 + 1) - \leq X_6$
Week 52/EOT	X_{Last}^c	(Previous Feminine Product Returned Visit + 1)] – $\leq X_{Last}$

^a If feminine products are collected at more than 1 visit within a given visit window (Table 2), the last feminine product collection date will be used to define the time window. If the patient missed the previous visit, a planned study visit date will be used to calculate the window.

^b In the absence of feminine product collection due to amenorrhea the visit date when amenorrhea was reported will be used.

^c Date of last non-missing feminine product collection within the interval from (last dose date – 35) to (last dose date + 7 days) (see Section 7.2.2).

General Rules for Missing Data

Handling of missing data for the primary efficacy analysis is described in Section 7.2.4.

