9.3.3. Endometrial Biopsy

The protocol-specified endometrial biopsy procedure is performed at the Week 52 or Early Termination Visit in the extension study. Consensus readings were performed on all endometrial biopsies. Endometrial biopsies will be summarized according to primary diagnosis categories

from the consensus reading (Table 15). Endometrial biopsies performed in the parent studies and in the extension study at Week 52 or at the time of early termination will be summarized. Any repeat endometrial biopsies performed will also be summarized. All endometrial biopsy data will also be provided in a by-patient listing, including visits in both the parent study and extension study.

Table 15: Categories of Primary Diagnosis in Endometrial Biopsies

Category	Diagnosis
Atrophy/Inactive	
 Limited surface endometrium Atrophy Inactive
Proliferative	
 Weakly proliferative Active proliferative Disordered proliferative pattern
Mixed	
 Mixed proliferative and secretory
Secretory/Menstrual	
 Secretory cyclic type Secretory progesterational type (including stromal decidualization) Non secretory endometrium with breakdown Menstrual
Reactive/Inflammatory	
 Chronic Endometritis Acute Endometritis
Polyp	
 Polyp, atrophic Polyp, functional Polyp, hyperplastic Polyp, adenomyomatous Polyp, other
Hyperplasia	
 Hyperplasia, simple, without atypia Hyperplasia, complex, without atypia Hyperplasia, simple, with atypia Hyperplasia, complex, with atypia
Carcinoma	
 Malignant carcinoma Malignant sarcoma Malignant mixed Mullerian tumor Malignant, other
Other	
 Benign tumor Other non-physiologic epithelial changes

Other: cannot classify based on provided information	—
Inadequate	
 • No specimen in container: verified by pathologist • Tissue unsatisfactory for diagnosis: no endometrium present • Tissue unsatisfactory for diagnosis: too scant for reliable diagnosis

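### SAP 4.3.8 gives some protocol-required early-termination assessments no place in any by-visit summary or model

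*SAP*

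**What the plan says.** SAP 4.3.8 states that visit windows "will be used only for summarizing data by visit". One result per window is kept: where there are several, "the non-missing result from the assessment closest to the target date will be used", and "If two assessments are equally close to the target day, the earlier assessment will be used".

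- Table 3 (bone density) and Table 5 (UFS-QoL) have contiguous late rows: "Week 36 197 253 308" and "Week 52 309 365 421" (start, target and end day).
- Table 4 (ECG) and Table 6, titled "Visit Windows for Week 24 and 52 Assessments (Transvaginal Ultrasound, EQ-5D-5L, Endometrial Biopsies"), have no Week 36 row. Week 24 ends on Day 196 and Week 52 starts on Day 309.
- Tables 5 and 6 add a Safety Follow-up row, from 7 to 60 days after the last dose. Tables 3 and 4 do not.

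Protocol 6.3 says "The Early Termination visit procedures are identical to those of Week 52". It then waives ultrasound, bone densitometry and biopsy when the last dose fell in Week 32 or earlier. The footnotes to the Schedule of Activities place the last dose in the clinic at the ET visit itself.

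The windows also feed the models. SAP 7.1.2 computes the mixed-model response from them. SAP 9.3.4 models bone density at Weeks 12, 24, 36 and 52 only, SAP 7.3.5 fits the volume ANCOVA at Week 52, and SAP 7.4.1 summarizes EQ-5D-5L at Baseline, Week 24 and Week 52. SAP 9.3.3 says that biopsies taken "in the extension study at Week 52 or at the time of early termination will be summarized".

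**The concern.** The protocol asks a woman who stops early to undergo the Week 52 assessments, so that her status at the end of treatment is on record. The window tables then give several of those results nowhere to go. The values left out are the last on-treatment bone density, uterine and fibroid volume, and EQ-5D-5L of women who did not finish. In a long-term extension whose named safety endpoints include bone density, that is the group a reader will ask about.

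The SAP also treats its endpoints unevenly. Menstrual blood loss has a Week 52/EOT window (Table 7), and SAP 9.2 summarizes selected laboratory tests on the last on-treatment observation. SAP 9.3.4 reports bone recovery in women selected on their loss at Week 52/EOT, yet no bone density table shows the EOT value for a woman who stopped before Day 309.

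**Working it through.** There is no sample size or power figure to reproduce. The check maps study days onto the window tables.

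**Target days.** Target = 7 x week + 1. Week 24: 169. Week 36: 253. Week 52: 365. These match the SAP.

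**The gap in Tables 4 and 6.** Days after 196 and before 309 are Days 197-308: 308 - 197 + 1 = 112 days. From Day 169 to Day 365 there are 365 - 169 + 1 = 197 days, so the gap covers 112/197 = 57% of the extension.

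**What is required in the gap.** ECG and EQ-5D-5L are required at every ET visit. Ultrasound is required only if the last dose came after Week 32. Depending on how Week 32 is counted, that begins on Day 225 or Day 232, which leaves 308 - 225 + 1 = 84 or 308 - 232 + 1 = 77 days.

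**Does Safety Follow-up catch them?** With the last dose at the ET visit the lag is 0 days, and a lag of 0-6 days maps to nothing. A lag of 7-60 days maps to Safety Follow-up for ultrasound and EQ-5D-5L. Table 4 has no such row, so an ECG in the gap never maps.

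**Two DXAs in the Week 36 window.** The protocol allows Week 36 plus or minus 7 days, Days 246-260 when counted from parent Day 1. Take the worst placed case: Week 36 scan on Day 246, ET scan on Day 260. The distances are |246 - 253| = 7 and |260 - 253| = 7, a tie, so the earlier scan is kept. Running every pair:

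| Week 36 scan | ET scan | ET scan kept |
|---|---|---|
| Days 246-260 | Days 260-308 | 0 of 734 pairs |
| Days 246-260 | Days 247-308 | 49 of 825 pairs, all with ET by Day 259 |
| Days 236-280 | Days 260-308 | 55 of 1,974 pairs, all with ET by Day 269 |

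The last row counts Week 36 from an actual Week 24 visit anywhere in its allowed range, Days 159-189: 159 + 84 - 7 = 236 and 189 + 84 + 7 = 280. Table 5 has the same late windows, so UFS-QoL behaves alike. If there is no usable Week 36 scan, the ET scan fills the slot and is not lost.

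**Illustrative size.** The documents give no discontinuation rate. Assume 200 women per parent group (one third of about 600), 10-30% stopping early, and stopping spread evenly over the 197 days:

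- ECG and EQ-5D-5L: 112/197 x 200 x 0.10 to 0.30 = 11 to 34 women.
- Required ultrasound: 77/197 x 200 x 0.10 = 8, to 84/197 x 200 x 0.30 = 26 women.
- Last DXA (Days 260-308, 49 days): 49/197 x 200 x 0.10 to 0.30 = 5 to 15 women, if all had a usable Week 36 scan.

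**The case against.** The strongest reply is that the windows do what they should. The volume and bone density endpoints are changes to Week 52, and an ultrasound on Day 230 does not belong in a Week 52 estimate. Closest-to-target is a sound prespecified rule. The study is descriptive, with no formal testing. All of that stands; it justifies keeping these values out of Week 52, but not having no place for them.

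Four stronger readings are tempting, and the documents do not support them.

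- *The data are discarded.* Windows govern by-visit summaries and the models built on them. Shift summaries use all values (SAP 4.3.8), and ECGs in the gap still count in the maximum post-Baseline QTcF analysis and the listings (SAP 9.3.1). ET biopsies are promised in SAP 9.3.3, so for them the fault is an inconsistency with Table 6.
- *Women withdrawn for bone loss lose the scan that showed it.* The scheduled DXAs before Week 52 are at Weeks 24 and 36, and an unscheduled one needs sponsor approval unless urgent (Protocol 6.5). The triggering scan is therefore normally one that the rule keeps. After a Week 36 scan on Days 246-260, the kept value is at most 308 - 246 = 62 days older than the dropped one.
- *The missing-at-random assumption of the bone density model fails.* Dropping a second value from one window does not by itself break it, and no bias can be quantified from the documents.
- *The volume ANCOVA is close to a completers analysis.* The Week 52 window opens on Day 309, 365 - 309 = 56 days before target, so women assessed at stopping on Days 309-364 are included.

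Poor response is also handled for the primary endpoint: SAP 7.2.4 counts withdrawals for lack of efficacy or fibroid surgery as non-responders.

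**Conclusion.** The concern holds as a gap in reporting. An ET ECG on Days 197-308 enters no by-visit table. The same is true of an ET EQ-5D-5L, and of a required ET ultrasound, unless it was done 7-60 days after the last dose; the ultrasound also stays out of the volume ANCOVA. A woman with a usable DXA or UFS-QoL near Day 253 who stops by Day 308 normally has her ET value dropped, so her last on-treatment bone density appears in no by-visit summary, decline category or model.

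The Group A mean change in lumbar spine density at Week 52, which the protocol compares with -2.2%, does not change, because a scan before Day 309 would not enter it anyway. The 112-day gap and the pair counts follow from the SAP and the protocol's visit windows. The counts of women rest on assumed group size, stopping rate and timing, and say nothing about the effect on any estimate. This is a worthwhile, inexpensive improvement; it does not show that a planned result is biased.

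**What to change.** Add a labelled *End of treatment* row to SAP Tables 3-6. Define it as the last on-treatment value after the first extension dose, up to last dose + 6 days (the Week 52 limit in Table 2), or + 30 days for DXA (the exclusion limit already in Table 3). Summarize it beside Week 52 for ECG, ultrasound, EQ-5D-5L, UFS-QoL, biopsy and bone density, including the bone density decline categories.

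Keep closest-to-target for the Week 36 slot. Replacing it with the last on-treatment value for women who discontinue would label scans as late as Day 308 as Week 36 for them alone, so that measurement time would depend on dropout.

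Repeat the uterine and fibroid volume ANCOVA with the end-of-treatment value as a sensitivity analysis. While editing the section, correct its text, which points to Table 6 for the UFS-QoL windows that stand in Table 5.

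The cost is SAP wording, extra table columns and one more model run; the data are already collected. The drawback is that end-of-treatment values mix treatment durations, so the tables must say so and should not be read as Week 52 results.

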- ^a The week 52 visit must occur on or after the 1-year anniversary of Study Day 1 in the parent study. The timing of the visit should also be at least 28 weeks (± 10 days) from the actual date of the Week 24/Baseline visit.
- ^b Unscheduled visits may be conducted at the investigator's discretion when needed. The reason for the visit will be captured in the source documents.
- ^c The Follow-up visit may be waived if the patient enrolls directly into another relugolix clinical study upon completion of the Week 52 visit.
- ^d May be signed up to 30 days prior to the Week 24/Baseline visit or during the Week 24/Baseline visit. Enrollment in MVT-601-3003 is defined by administration of the first dose of MVT-601-3003 study drug.
- ^e Record all prescription and nonprescription drug and supplements taken from the Week 24/Baseline visit through the Safety Follow-Up period. Concomitant medications with start date prior to the first dose of study drug for MVT-601-3003 should be reported as concomitant medications in the parent study (MVT-601-3001 or MVT-601-3002). Concomitant medications initiated during the MVT-601-3001 or MVT-601-3002 studies and ongoing at the time of the first dose in Study MVT-601-3003 will be recorded in the electronic case report form.
- ^f Concomitant medications are recorded both for the parent study and for MVT-601-3003 at the Week 24/Baseline visit. (See footnote c for further details).
- ^g This is a parent study (MVT-601-3001 or MVT-601-3002) Week 24 procedure that serves as the Week 24/Baseline procedure for MVT-601-3003 and is covered under the informed consent for the parent study.
- ^h The indicated procedure may be performed at the Unscheduled visit based on the purpose of the visit (eg, follow-up for an adverse event or abnormal laboratory test).
- ⁱ See parent study protocols (MVT-601-3001 or MVT-601-3002) for instructions on testing visual acuity.
- ^j The exam may include a gynecologic examination, if indicated based on signs and symptoms.
- ^k The 12-lead ECGs will be submitted for central reading.
- ^l Clinical laboratory tests at each visit include clinical chemistries and a complete blood count. At the Week 24/Baseline visit and Week 52 visit, additional tests include: fasting (at least 8 hours) glucose, lipid profile, and hemoglobin A1c.
- ^m Samples should be obtained in a fasted state (at least 8 hours). Water is allowed during the fasting period.

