
6.6.1.3. Endometrial Biopsy

Per the parent study MVT-601-3001 protocol, an endometrial biopsy is performed for all subjects at the Week 24 visit, whereas per the parent study MVT-601-3002 protocol, an endometrial biopsy is performed at the Week 24 visit only if indicated (endometrial thickness at any location is ≥ 4 mm or if any other endometrial abnormality is visualized on the Week 24 ultrasound). If the required Week 24 biopsy is inadequate for diagnosis, it should be repeated, and a sample submitted to the central laboratory. If the second sample is inadequate, ensure an endometrial thickness has been reported from the Week 24 transvaginal ultrasound and contact the medical monitor to review the findings. Patients who have endometrial hyperplasia or endometrial carcinoma, will be withdrawn from study drug treatment and followed per instructions in the parent study protocol.

Additional assessment of the effects of relugolix co-administered with low-dose estradiol and norethindrone acetate on the endometrium will be performed at Week 52 and submitted to the central laboratory. If the Week 52 biopsy specimen is inadequate, the endometrial thickness reported at the Week 52 transvaginal ultrasound will be used to determine if further action is required:

- Endometrial thickness ≤ 5 mm – no further action required.
- Endometrial thickness > 5 mm at any location or any other endometrial abnormality – repeat endometrial sampling. Contact medical monitor if second specimen is inadequate for diagnosis.

Patients who decline endometrial sampling at Week 52 will not be prohibited from participating in the randomized withdrawal study.

Unscheduled endometrial biopsies may also be performed when medically indicated and as deemed necessary by the investigator. The investigator should obtain approval from the sponsor to perform an unscheduled endometrial biopsy, unless urgently indicated. Additional consent is not required in this circumstance.

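### Picking one endometrial biopsy per window by closeness to Day 365 can keep an inadequate Week 52 sample over its adequate repeat, and can let a follow-up biopsy displace hyperplasia

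*SAP*

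**What the plan says.** **Selection rule (SAP 4.3.8).** Visit windows "will be used only for summarizing data by visit". Within a window, "the non-missing result from the assessment closest to the target date will be used". For ties, "If two assessments are equally close to the target day, the earlier assessment will be used".

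**Biopsy windows (SAP Table 6).** Endometrial biopsies share a table with ultrasound and EQ-5D-5L. Week 52 runs from Day 309 to Day 421 with target Day 365. Safety Follow-up runs from 7 to 60 days after the last dose.

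**Categories (SAP 9.3.3, Table 15).** *Inadequate* is one of the primary-diagnosis categories and includes readings such as "Tissue unsatisfactory for diagnosis: too scant for reliable diagnosis". The section adds: "Any repeat endometrial biopsies performed will also be summarized". It also provides a by-patient listing of all biopsies. It does not say whether a repeat replaces an inadequate result at its visit.

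**Repeats (Protocol 6.6.1.3).** "If the Week 52 biopsy specimen is inadequate, the endometrial thickness reported at the Week 52 transvaginal ultrasound will be used" to decide on further action. Sampling is repeated when thickness exceeds 5 mm or another abnormality is seen. No time limit for the repeat is given.

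**Timing (Protocol 1.1, Schedule of Activities, footnote a).** "The week 52 visit must occur on or after the 1-year anniversary of Study Day 1 in the parent study".

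**Follow-up of a diagnosis (SAP 3.3).** Women not entering MVT-601-035 who have hyperplasia or cancer on biopsy are to have a repeat 3 to 6 months after the Week 52 or Early Termination visit.

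**The concern.** Closeness to a target day is a sensible tie-breaker for a quantity measured repeatedly with error. It suits a pathological diagnosis poorly: a failed sample carries no diagnosis, and a biopsy taken after treatment has stopped answers a different question from one taken on treatment.

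Repeats after an inadequate Week 52 specimen are required only in women whose endometrium is thick or looks abnormal. These are the women in whom the diagnosis matters most. If hyperplasia is expected in very few women, a single case missing from the Week 52 row could change how that row is read.

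The SAP avoids this elsewhere in safety. It uses all values for shift summaries (4.3.8), the worst post-Baseline toxicity grade (9.2) and the maximum post-Baseline QTcF (9.3.1). Biopsies have no comparable rule.

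**Working it through.** The plan states no figure on this point to reproduce. The check applies the 4.3.8 rule to pairs of biopsy days. Table 6's target agrees with 52 × 7 + 1 = 365.

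**1. Completers, with *Inadequate* treated as non-missing**
- The Week 24 visit falls on Day 169 − 10 = 159 to 169 + 20 = 189.
- Adding 28 weeks (196 days) gives Day 355 to 385, and the 10-day allowance extends this to Day 395. The anniversary requirement raises the lower end to Day 366.
- Let the first sample be on day d ≥ 366 and the repeat L ≥ 1 days later. The distances from target are d − 365 and d + L − 365. The repeat is further away by exactly L days, so the first sample is always kept.
- Over d = 366 to 395 and L = 1 to 60 (an assumed range, since no lag is given), the first sample is kept in all 30 × 60 = 1,800 combinations. In 1,215 the repeat is in the window but further from target. In 585 it falls after Day 421.

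**2. Completers, with *Inadequate* treated as missing**
- The adequate repeat is selected if it falls by Day 421. That allows a lag of up to 421 − 366 = 55 days for a first sample on Day 366, and 421 − 395 = 26 days for one on Day 395.
- The coding choice therefore decides the Week 52 row, and the SAP does not make it.

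**3. Early termination, inadequate sample on Days 309 to 364**
- Over the same lags there are 56 × 60 = 3,360 combinations. The repeat is closer to target, and so selected, in 2,460 (73%). For example, a first sample on Day 320 with a 28-day lag selects the repeat. A first sample on Day 351 with a 28-day lag ties (14 days each side) and keeps the first.
- These are counts of day-and-lag combinations, not probabilities for patients.

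**4. Early termination with hyperplasia, then a repeat under SAP 3.3**
- Both specimens are adequate, so the coding of *Inadequate* is irrelevant.
- Three months is 3 × 30.4375 ≈ 91 days. A repeat at d + 91 is closer to target than d when d + 91 − 365 < 365 − d, that is d < 319.5.
- With d = 310 the repeat is on Day 401. The distances are 55 and 36 days, so the post-treatment result replaces the hyperplasia.
- At the start of the window (d = 309) the original is 56 days from target, so displacement needs a lag below 2 × 56 = 112 days. The exposed range is therefore about Days 309-319, with repeats early in the 3-to-6-month period.
- For bone mineral density, Table 3 excludes assessments more than 30 days after the last dose. Table 6 has no such exclusion for its Week 52 window.

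**5. Overlap with Safety Follow-up**
- The last dose is taken at the Week 52 visit. With a last dose on Day 366, Safety Follow-up runs from Day 373 to Day 426 and overlaps the Week 52 window on Days 373-421. No rule says which visit takes a repeat in the overlap.

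**The case against.** The strongest reply is that nothing is lost from the report. Repeats are summarized, every biopsy is listed, and windows affect by-visit displays only. Malignancy also has its own route: Protocol 7.1.2 gives invasive or malignant cancers as examples of serious adverse events, and SAP 9.1 tabulates those. The study is descriptive, with no inferential statistics. All of this stands, and it limits the point to the Week 52 row.

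Three stronger readings are tempting, and the documents do not support them:
- **That the SAP classifies such cases as *Inadequate* at Week 52.** It never says an inadequate specimen is non-missing, and early terminations before Day 365 often select the repeat.
- **That the repeat would appear only in a separate summary.** SAP 9.3.3 does not call the summary separate. A completer sampled on Day 368 and repeated on Day 390 is 22 days past last dose, inside a Safety Follow-up window of Days 375-428, unless another agent, hormonal therapy or surgery came first.
- **That 3 to 48 women would be affected.** This comes from 600 × 5% × 10% = 3 and 600 × 20% × 40% = 48. Both shares are assumptions. The base of 600 treats every woman as biopsied with an adequate, in-window repeat. The protocol lets women decline, waives the biopsy at early termination when the last dose was in Week 32 or earlier, and allows for a second inadequate specimen.

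Counting inadequate samples in the denominator is also largely a display choice, because their number has its own row.

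**Conclusion.** The selection rule is unsuited to biopsies and should be changed, though the consequence is narrower than missing diagnoses. For on-schedule completers, and on the natural but unstated reading that *Inadequate* is non-missing, the failed sample is always the Week 52 result. Hyperplasia or carcinoma found on the required repeat is then absent from that row, while remaining in the summary of repeats, the listing and possibly the Safety Follow-up row. If *Inadequate* is treated as missing, this problem remains only for repeats after Day 421.

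The displacement of hyperplasia by a post-treatment repeat, for early terminations on about Days 309-319, does not depend on that coding. It matters only if the repeat gives a different diagnosis.

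The number affected cannot be derived: the documents give no inadequate rate, no share meeting the repeat criterion and no repeat lag. The argument that the first sample is always kept applies to Week 52 only; at Week 24 the first sample can fall on either side of Day 169.

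**What to change.** In SAP 9.3.3, exempt biopsies from the closest-to-target rule in 4.3.8 and state:

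1. An inadequate specimen counts as missing for visit selection whenever an adequate specimen exists.
2. If more than one adequate specimen falls in the window, the most severe diagnosis is used.
3. A repeat taken because the Week 52 or Week 24 specimen was inadequate is assigned to that visit and not to Safety Follow-up. Follow-up biopsies under SAP 3.3 never replace the on-treatment result.
4. Optionally, percentages with hyperplasia and carcinoma are also shown among women with an adequate specimen.

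Item 3 settles the overlap with Safety Follow-up and also covers repeats that fall after Day 421. The cost is SAP wording and minor programming. No extra biopsies or readings are needed, and clinical procedures do not change.
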